### **9.3. Determination of Sample Size**

A sample size of approximately 100 patients who receive two doses of FX006 is considered a reasonable sample size in order to assess the safety profile of repeat administration of FX006. No formal power and sample size calculations have been made as the analysis of the efficacy data collected from this study will be considered exploratory and hypothesis-generating for future multiple dose studies of FX006. In order to ensure at least 100 patients who receive two doses of FX006 are enrolled and followed for 52 weeks, approximately 200 patients will be enrolled based on an estimate that approximately 66% of patients enrolled will be eligible to receive a second dose of FX006 and approximately 75% of subjects who receive a second dose will complete the study through Week 52.

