#### **9.4.2. Exposure**

Treatment exposure will be listed by study site and patient, and will be summarized by doses administered, as well as total exposure to FX006. Time between FX006 exposure (1st and 2nd doses) will be summarized.

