#### **9.4.4. Safety Analyses**

AEs will be coded using the Medical Dictionary for Regulatory Activities (MedDRA) dictionary. Incidences (number and percent) TEAEs, those events that started after dosing or worsened in severity after dosing, will be presented by treatment group. Incidences of TEAEs will also be presented by maximum severity and relationship to study medication. Similar presentations will be provided for serious AEs, AEs leading to withdrawal from the study, or AEs leading to death.

Analysis of AE data will include examination of the incidence rates and changes in severity of TEAEs and index knee related TEAEs following the first dose and second dose, as well as the cumulative incidence of TEAEs after all doses of FX006. Both the number of events and the number of patients experiencing an event will be examined to assess the by patient cumulative incidence of TEAEs associated with repeat administration. The cumulative TEAE incidence rate will also be compared with total exposure to FX006.

Clinical laboratory data and vital sign information will be presented as descriptive summary statistics for value and change from Baseline at each individual time point.

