### 1.2. Objectives of Statistical Analysis

#### 1.2.1. Primary Objective

The primary objective of this study is to assess the overall safety and general tolerability of repeat administration of FX006 (two doses of 32 mg FX006) in patients with symptomatic OA of the knee.

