#### 4.10.1. Adverse Events

Adverse events will be coded using the MedDRA (version 19.1) coding system and displayed in tables and data listings using system organ class (SOC) and preferred term (PT).

Analyses of AEs will be performed for those events that are considered treatment-emergent, where treatment-emergent is defined as any AE with onset after the administration of study treatment, or any event that was present at baseline but worsened in intensity through the end of the study.

If the start date/time of an AE is partially or completely missing, the date/time will be compared as far as possible with the date/time of the start of administration of study drug. The AE will be assumed to be treatment emergent if it cannot be definitively shown that the AE did not occur or worsen during the treatment-emergent period (worst case approach). The following general rules will be used:

- If the start time of an AE is missing but the start date is complete, an AE will only be excluded as being treatment emergent if the start date is before the date of study drug administration or if the stop date/time is before study drug administration.
- If the start time and day are missing but the start month and year are complete, an AE will only be excluded as being treatment emergent if the start month/year is before the month/year of study drug administration or if the stop date/time is before study drug administration.
- If the start day and month are missing but the start year is complete, an AE will only be excluded as being treatment emergent if start year is before the year of study drug administration or if the stop date/time is before study drug administration.
- If the start date is completely missing, an AE will be considered treatment-emergent unless the stop date/time is before study drug administration.

Adverse events will be summarized by patient incidence rates; therefore, in any tabulation, a patient contributes only once to the count for a given SOC or preferred term.

Summary tables will display the number and percentage of patients who experienced at least one TEAE in each of the following categories:

- Any TEAE
- Any Serious Adverse Event (SAE)
- Any TEAE leading to study discontinuation
- Any TEAE by severity (grade 1-5)
- Any TEAE by relationship
- Any index-knee related TEAE
- Any index-knee related SAE
- Any index-knee related TEAE leading to study discontinuation

- Any index-knee related TEAE by severity (grade 1-5)

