- Any index-knee related TEAE by relationship
- Any TEAE related to injection procedure

Separate tabulations will be produced for each of following categories:

- All TEAEs by SOC and PT
- All SAEs by SOC and PT
- All TEAEs related to study drug by SOC and PT
- All TEAEs related to injection procedure by SOC and PT
- All TEAEs by maximum severity by SOC and PT
- All TEAEs leading to study discontinuation
- All TEAEs leading to death
- All index-knee related TEAEs by SOC and PT
- All index-knee related TEAEs related to study drug by SOC and PT
- All index-knee related TEAEs by maximum severity by SOC and PT

Summary tables and the tabulation of All TEAEs by SOC and PT will be presented for the following patient groups and time periods, with a separate table for each patient group:

1. Patients receiving only one dose
  - a. First dose to Week 12
  - b. First dose to Week 24 (end of study)
2. Patients receiving the second dose at Week 12
  - a. First dose to Week 12
  - b. Week 12 to Week 24
  - c. Week 12 to Week 52
3. Patients receiving the second dose at Week 16
  - a. First dose to Week 16
  - b. Week 16 to Week 32
  - c. Week 16 to Week 52
4. Patients receiving the second dose at Week 20
  - a. First dose to Week 20
  - b. Week 20 to Week 40
  - c. Week 20 to Week 52
5. Patients receiving the second dose at Week 24
  - a. First dose to Week 24
  - b. Week 24 to Week 48
  - c. Week 24 to Week 52

Summary tables and all tabulations will be presented for the following time periods for patients receiving two doses only (same table):

1. Baseline to Week 52
2. Baseline to Week 12
3. Second dose to 12 weeks after second dose

Date and time of onset of TEAE will be used to assign the time periods.

In the summary table for "Any TEAE by SOC and PT", an additional row with the number of events observed will be presented. A patient will be counted once for the number of patients if they have multiple events. The total number of events will be the absolute number of events observed, and a patient will be counted more than once for the event totals if they have multiple events.

In these tabulations, related is defined as any TEAE deemed possibly, probably or definitely related to study drug by the investigator. If relationship is missing, it will be imputed as related.

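### SAP 4.10.1 gives TEAEs no time-at-risk denominator and drops the Protocol 9.4.4 exposure comparison without saying so, so the windows to Week 52 are not comparable as crude percentages

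*SAP*

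**What the plan says.** Safety is the primary objective (SAP 1.2.1): "The primary objective of this study is to assess the overall safety and general tolerability of repeat administration of FX006".

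Protocol 9.4.4 plans TEAE incidence after the first dose and after the second, "as well as the cumulative incidence of TEAEs after all doses of FX006", counted both by event and by patient. It then adds: "The cumulative TEAE incidence rate will also be compared with total exposure to FX006". Under Protocol 9.4.2, treatment exposure "will be summarized by doses administered, as well as total exposure to FX006".

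SAP 4.10.1 sets the measure: "Summary tables will display the number and percentage of patients who experienced at least one TEAE in each of the following categories". It also says: "Adverse events will be summarized by patient incidence rates; therefore, in any tabulation, a patient contributes only once to the count". The table by system organ class and preferred term gains a row with the number of events. The windows are:

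- **One-dose patients:** first dose to Week 12, and first dose to Week 24.
- **Each re-dosing group (Week 12, 16, 20, 24):** a matched pair of 12/12, 16/16, 20/20 or 24/24 weeks, plus a window from second dose to Week 52, for example "Week 12 to Week 52".
- **All two-dose patients:** Baseline to Week 52, Baseline to Week 12, and second dose to 12 weeks later.

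SAP 4.10.1 gives no denominator for any window, and no patient-time, rate or time-to-event estimate. SAP 4.8 covers injection details, numbers given one or two doses, and time to second dose, but not total exposure. SAP Section 5 lists two changes: the one-dose versus two-dose comparisons are dropped, and the Kaplan-Meier endpoint is replaced.

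On loss to follow-up, Protocol 9.3 expects that "approximately 75% of subjects who receive a second dose will complete the study through Week 52".

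**The concern.** A percentage of patients with an event depends on how long they were observed as well as on their risk. Two features of the design make observation time unequal.

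1. All two-dose patients stop at Week 52 whenever they were re-dosed, so follow-up after dose 2 shortens as re-dosing moves later. Similarly, the one-dose window to Week 24 includes patients without benefit, who finish at Week 12 (SAP 2.1).
2. A patient is in the two-dose group only if still in the study at re-dosing. The first-dose window of each pair therefore has no loss, while the second-dose window can lose patients.

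Without time at risk, a reader cannot tell a difference in risk from a difference in follow-up. The analysis the protocol tied to exposure is absent, although SAP 1.2.2 says the SAP will set out differences from the protocol's planned analytical objectives.

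**Working it through.** **Check on the planning figure.** 200 enrolled × 0.66 × 0.75 = 99, which agrees with the stated target of about 100 two-dose completers. The 75% completion figure is therefore used as the plan uses it. The documents give no figure for the TEAE measure itself, so the rest is illustration.

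**Inputs**

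- TEAE incidence: 46.0% of FX006 patients (Protocol 5.2.8). No follow-up length is stated, so both 12 and 24 weeks are tried (assumption).
- Constant hazard: λ = −ln(1 − 0.46)/12 = 0.05135 per week, or −ln(1 − 0.46)/24 = 0.02567 per week (assumption).
- Loss after dose 2: 25% by Week 52, spread exponentially, d = −ln(0.75)/(52 − re-dosing week) per week (assumption on timing).
- Early leavers contribute no later AEs and stay in the denominator (assumption).

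**Formulas.** True risk over w weeks is 1 − exp(−λw). The crude percentage with loss is λ/(λ+d) × [1 − exp(−(λ+d)w)].

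**Second dose to Week 52.** Worked for the 24-week reading:

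- Week 12 group: d = 0.28768/40 = 0.00719; crude = 0.02567/0.03287 × [1 − exp(−0.03287 × 40)] = 57.1%.
- Week 24 group: d = 0.28768/28 = 0.01027; crude = 0.02567/0.03595 × [1 − exp(−0.03595 × 28)] = 45.3%.

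| Re-dosing week | Window (weeks) | Mean follow-up (weeks) | No loss, 12-wk / 24-wk reading | With 25% loss, 12-wk / 24-wk reading |
|---|---|---|---|---|
| 12 | 40 | 34.8 | 87.2% / 64.2% | 79.3% / 57.1% |
| 16 | 36 | 31.3 | 84.3% / 60.3% | 76.3% / 53.6% |
| 20 | 32 | 27.8 | 80.7% / 56.0% | 72.8% / 49.6% |
| 24 | 28 | 24.3 | 76.3% / 51.3% | 68.5% / 45.3% |

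The gap between the Week 12 and Week 24 groups is 79.3 − 68.5 = 10.8 points, or 57.1 − 45.3 = 11.8 points, although the hazard is the same in every row. With no loss it is 10.9 or 12.9 points, so window length, not dropout, creates it.

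**Matched windows.** Loss within 12 weeks of dose 2 is 8.3% to 11.6%, depending on group.

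| Pair | Dose 1, 12-wk / 24-wk reading | Dose 2 with loss | Difference (points) |
|---|---|---|---|
| 12 weeks, any group | 46.0% / 26.5% | 43.5–44.3% / 25.0–25.5% | 1.7–2.5 / 1.0–1.5 |
| 24 weeks, Week 24 group | 70.8% / 46.0% | 64.3% / 41.3% | 6.5 / 4.7 |

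**What a rate would show.** Expected time at risk for a first event is [1 − exp(−(λ+d)w)]/(λ+d). On the 24-week reading this is about 22.3 weeks per patient in the Week 12 group and 17.7 weeks in the Week 24 group. Dividing the crude risk by it gives 0.571/22.3 and 0.453/17.7, both about 2.57 first events per 100 patient-weeks before rounding. On the 12-week reading the common rate is 5.13. The rate recovers the equal risk that the percentages hide.

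**The case against.** The case for leaving the plan largely alone has real content.

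- **Percentages are not the only output.** A reader might infer that they are, but event counts are also tabulated. The counts are not rates, so the missing time at risk remains.
- **The main contrast is matched.** A reader might take all the windows to be unequal. They are not: every re-dosing group has an equal nominal pair, and the pooled two-dose table sets 12 weeks against 12 weeks. On the 24-week reading, the 12-week effect of 1.0 to 1.5 points is under half the standard error of a 26.5% proportion: √(0.265 × 0.735/180) = 3.3 points with 180 two-dose patients (90% of 200), and 3.8 points with 132 (66% of 200). This stands.
- **The protocol does not promise patient-years.** Total exposure to FX006 can be read as amount of drug. At a fixed dose given once or twice, that is nearly one dose versus two, a comparison Section 5 drops for safety with a reason. This is arguable, but Section 5 neither says so nor mentions the exposure sentence. If exposure means time, Section 5 does not cover it at all.
- **The denominator and the loss are uncertain.** A reader might assume the full Safety Population is the denominator in every window and that all dropout is lost to AE follow-up, so that dose 2 risk is understated. Neither is established. SAP 4.10.1 is silent on window denominators, and the table shells are in a separate document. Protocol 7.4.4 allows willing patients who leave after a second injection to be contacted for AEs through Week 52, whereas footnote 17 of Protocol Table 1 ends capture at the early discontinuation visit. Those two texts need reconciling, because they determine time at risk.
- **Rates have limits.** FX006 is intended to release drug for about 3 months, so the hazard may not be constant and a 40-week average could dilute early risk. Nor does patient-time remove selection: re-dosing required benefit and no major safety concern. This is why rates should supplement the matched percentages, not replace them.
- **No formal inference is at stake.** Hypothesis tests of AE rates are excluded, each group has its own table, and only about 10 patients had one dose. This limits the consequence without making the unequal windows interpretable.

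**Conclusion.** The point holds in limited form. The SAP has no time-at-risk summary for TEAEs, and it omits the Protocol 9.4.4 exposure comparison without recording this in Section 5. The practical effect is on the windows from second dose to Week 52, where groups with identical risk would read about 11 to 12 points apart, and on the one-dose window to Week 24, which mixes two lengths of follow-up.

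The matched dose 1 versus dose 2 windows are sound on paper. One-sided dropout would shift them by an illustrative 1.0 to 2.5 points at 12 weeks and 4.7 to 6.5 points in the 24-week pair, provided early leavers are lost to AE follow-up and kept in the denominator.

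All sizes rest on a constant hazard, 46% with a TEAE over an assumed 12 or 24 weeks, and the planned 25% loss. That loss is a planning value; the companion estimate of 66% re-dosed has been overtaken by more than 90% (SAP Section 5). The documents do not support reading this as a general failure of the dose 1 versus dose 2 safety comparison. The change should be made, but the omission does not undermine the trial's main safety display.

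**What to change.** In SAP 4.10.1:

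1. State the denominator for each window and how patients who leave early are counted, consistent with a reconciled reading of Protocol 7.4.4 and Table 1 footnote 17.
2. Beside the existing percentages, add patient-time at risk, and first-event and total-event rates per 100 patient-years with 95% confidence intervals, for any TEAE, SAEs and index-knee TEAEs.
3. Say that these rates are to be used for the windows to Week 52 and for reading across timing groups, and that the matched-window percentages remain the main dose 1 versus dose 2 display.

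Separately, restore the Protocol 9.4.4 comparison of cumulative TEAE incidence with total exposure, with exposure defined, or list its removal and the reason in Section 5. Patient-year rates alone would not restore a comparison based on amount of drug.

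The cost is a few table columns and some lines of text. The SAP already uses onset dates to assign events to windows, so no new data are needed. The drawback is that each rate averages over a hazard that may vary after injection, which a footnote should say.

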**Unscheduled visit windowing:**

If a patient receives their second dose of study medication at an unscheduled visit that is not  $>3$  weeks after Week 24, the dosing information and all other data collected at that visit will be mapped to the closest nominal visit, based on Rel Day Dose 1, even if data is already available in that visit. All data collected at the time of the second dose will be used for analysis. If data is available in the nominal visit, but was not collected at the unscheduled visit associated with the second dose, the data from the nominal visit will be used. If a patient receives their second dose at an unscheduled visit that is  $> 3$  weeks past Week 24, data from that unscheduled visit will not be used for time to second dose analyses or exploratory efficacy analyses involving two-dose patients.

Data collected at unscheduled visits that are not associated with the second dose will be mapped to the closest scheduled visit, but only if that data is not already available in that visit. Otherwise data will be summarized and presented according to the nominal visit as recorded on the Case Report Form (CRF).

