#### **4.7. Demographic and Baseline Characteristics**

Demographics and baseline characteristics will be summarized and presented for the SP for patients receiving only one dose, patients receiving two doses, and all patients combined. Age, height, weight, and body mass index (BMI) will be summarized using descriptive statistics (number of patients, mean, standard deviation, median, minimum, and maximum). Age will be calculated as the years between date of birth and date of informed consent, and will be rounded down to the nearest year. The number and percentage of patients in each gender, ethnicity and race category will also be presented. Additionally, for two-dose patients only, demographic and baseline characteristic data will be presented separately based on the time at which the second dose was administered. These statistics will be presented for the following groups. Each group will be displayed as a different column in the same table, in this order:

1. Patients receiving the second dose at Week 12
2. Patients receiving the second dose at Week 16
3. Patients receiving the second dose at Week 20
4. Patients receiving the second dose at Week 24
5. Patients Receiving the Second Dose after Week 24

OA background characteristic data and index knee characteristic data as collected on the CRF will also be tabulated for the SP for all patients combined. Time from primary diagnosis of OA in the index knee to Day 1 of the study in years (dose date – date of diagnosis + 1)/365.25, will be computed and presented descriptively. Additionally, for two-dose patients only, OA background characteristic data and index knee characteristic data will be presented separately based on the time at which the second dose was administered. These statistics will be presented

for the following groups. Each group will be displayed as a different column in the same table, in this order:

1. Patients receiving the second dose at Week 12
2. Patients receiving the second dose at Week 16
3. Patients receiving the second dose at Week 20
4. Patients receiving the second dose at Week 24
5. Patients Receiving the Second Dose after Week 24

For all time to diagnosis calculations, if only month and year of initial diagnosis is available, day will be imputed as 1 for calculations. If month and day are missing, the time from primary diagnosis will be computed as year of administration of study treatment minus year of diagnosis. If year is missing, time from diagnosis will not be computed.

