If an event has a TEAE start date that, after imputation rules are applied, is not complete enough to determine the time period in which the TEAE occurred, that event will not be included in the tabulations by study day.

Formal hypothesis-testing of AE incidence rates will not be performed.

By-patient listings will be provided for the following, for all patients: patient deaths, SAEs and AEs leading to discontinuation.

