## 5. CHANGES TO PLANNED ANALYSES

In the original protocol the intended analysis was to compare the responses for those patients who received only a single dose to those patients who received two doses of FX006. During the study >90% of the patients enrolled have received a second dose, with approximately 10 patients only receiving one dose. This limited enrollment in a single dose does not adequately support making the protocol specified one-dose to two-dose comparisons for safety and exploratory efficacy meaningful. These comparisons have been eliminated from planned analyses.

According to the protocol, time to maximal pain relief response with WOMAC A (pain) following the first and second doses of FX006 would be examined using a Kaplan-Meier procedure. Instead, the time to second dose was examined using the Kaplan-Meier procedure as this provides a better indication of durability of first-dose response.

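### For all two-dose patients combined, no planned adverse-event column isolates the period from the second injection to Week 52; the only one starting at dose 2 stops at 12 of 28 to 40 planned weeks

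*SAP*

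**What the plan says.** The primary objective (Protocol 6.1, SAP 1.2.1) is the safety and tolerability of two doses. Protocol Table 1, note 17, collects adverse events to Week 52 in patients who receive a second injection, whichever of Weeks 12, 16, 20 or 24 they receive it at. Protocol 9.4.4 asks for TEAE and index-knee TEAE incidence after the first dose, after the second dose and cumulatively. It sets no 12-week limit.

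SAP 4.10.1 delivers this through two layouts.

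- **By re-dosing visit.** "Summary tables and the tabulation of All TEAEs by SOC and PT will be presented for the following patient groups and time periods". Each two-dose group (Week 12, 16, 20 or 24) has its own table, with a column from the second dose to Week 52. This layout covers the summary tables and one of the ten tabulations.
- **Pooled.** For all two-dose patients, the summary tables and all ten tabulations have three columns: Baseline to Week 52, Baseline to Week 12, and "Second dose to 12 weeks after second dose".

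The counting rule is that "in any tabulation, a patient contributes only once to the count for a given SOC or preferred term". On listings, "By-patient listings will be provided for the following, for all patients: patient deaths, SAEs and AEs leading to discontinuation". In addition, SAP 4.2.1 lists all collected data, and SAP 4.2.9 shows study day relative to dose 2 for dates after that dose.

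For late re-dosing, SAP 4.2.9 says that data from a second dose given at an unscheduled visit no more than 3 weeks after Week 24 "will be mapped to the closest nominal visit, based on Rel Day Dose 1". SAP 4.7 gives "Patients Receiving the Second Dose after Week 24" a column in the baseline tables. SAP 4.10.1 has no matching adverse-event table.

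**The concern.** A reader who wants to know what happened after the second injection will look first at the pooled two-dose tables. There, the only column that starts at dose 2 ends at 12 weeks. The column that reaches Week 52 also contains the 12 to 24 weeks before re-dosing, so first-dose and second-dose events cannot be told apart in it.

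The by-visit tables do isolate the full period, but not for nine tabulations. Three of those nine (SAEs, deaths, discontinuations) have dedicated by-patient listings, so little is missing there. The other six do not: drug-related, procedure-related, maximum severity, and the three index-knee tabulations.

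The index-knee tables are where late events are of most interest. In the repeat-dose dog study (Protocol 5.2.3), dosing every 3 months was followed by further cartilage changes at 6 months that were absent at 1 month. The protocol attributes these to known corticosteroid effects, and they occurred in males only and in both active groups. They still give a reason to want the pooled index-knee display to run past 12 weeks.

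**Working it through.** **The plan's own figure.** SAP 4.1 gives about 200 enrolled, 66% re-dosed, and 75% of those completing Week 52. 200 × 0.66 × 0.75 = 99, which agrees with the target of about 100 patients with two doses followed for 52 weeks. Long follow-up after dose 2 is therefore part of the design.

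**Share of follow-up in the 12-week column.** With dose 2 at week w, planned follow-up is F = 52 − w. The share inside is 12/F and the weeks outside are F − 12. Week 27 is added as the last week to which the mapping rule in SAP 4.2.9 applies. Visit windows of ±7 days shift these values slightly.

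| Dose 2 at week | F (weeks) | Inside, 12/F | Weeks outside | Share outside | Share outside if 25% leave at 12 weeks |
|---|---|---|---|---|---|
| 12 | 40 | 30.0% | 28 | 70.0% | 63.6% |
| 16 | 36 | 33.3% | 24 | 66.7% | 60.0% |
| 20 | 32 | 37.5% | 20 | 62.5% | 55.6% |
| 24 | 28 | 42.9% | 16 | 57.1% | 50.0% |
| 27 | 25 | 48.0% | 13 | 52.0% | 44.8% |

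The last column assumes that the 25% who do not complete all leave exactly 12 weeks after dose 2. That timing makes the outside share smallest. The formula is 0.75(F − 12) / [12 + 0.75(F − 12)]; for w = 12 it gives 21/33 = 63.6%.

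**Size in person-time.** SAP section 5 says "During the study >90% of the patients enrolled have received a second dose, with approximately 10 patients only receiving one dose". Assuming about 200 enrolled as planned, that is 180 to 190 two-dose patients. The 12-week column then holds 180 × 12/52 = 41.5 to 190 × 12/52 = 43.8 person-years. With complete follow-up, the total after dose 2 is 96.9 to 102.3 person-years if all are re-dosed at Week 24, and 138.5 to 146.2 if all are re-dosed at Week 12.

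**Can the missing column be obtained by subtraction?** No, for two reasons.

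1. Patients count once per term. Take someone re-dosed at Week 12 with the same term at Week 5 and again at Week 45. They count 1 in Baseline to Week 52, 1 in Baseline to Week 12, and 0 in the 12 weeks after dose 2. Subtraction gives 1 − 1 − 0 = 0, although a late event occurred.
2. The w − 12 weeks between Week 12 and dose 2 (4, 8 or 12 weeks for re-dosing at Week 16, 20 or 24) lie in neither short column.

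**Can it be obtained by adding the by-visit tables?** Yes, for the summary rows and All TEAEs by SOC and PT, because the four groups do not overlap. It fails for the other nine tabulations and for anyone outside the four groups. The midpoint between Weeks 24 and 28 is Week 26, so on a literal reading an unscheduled second dose between Weeks 26 and 27 maps to Week 28, which has no adverse-event group. Doses after Week 27 have none either. The documents give no count of such patients.

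**Why a rate should sit beside the percentage.** Assume a constant first-event rate and a 12-week incidence p. The crude percentage over F weeks is 1 − (1 − p)^(F/12).

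| p | 28 weeks | 40 weeks | Difference (points) |
|---|---|---|---|
| 10% | 21.8% | 29.6% | 7.8 |
| 20% | 40.6% | 52.5% | 11.9 |
| 30% | 56.5% | 69.5% | 13.0 |
| 40% | 69.6% | 81.8% | 12.2 |

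Follow-up length alone moves the percentage by about 8 to 13 points. These values of p are illustrative and are not in the documents.

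**The case against.** The best defence is that the full second-dose period is already planned. The by-visit tables run to Week 52 and carry every summary row: severity, relationship, seriousness, discontinuation, injection procedure, and the index-knee rows by severity and relationship. They also have intermediate columns reaching 16, 20 and 24 weeks after dose 2 in the Week 16, 20 and 24 groups. Keeping the groups separate avoids mixing 28 and 40 weeks of follow-up, which is the problem a pooled percentage creates. The 12-week column is also well chosen as a comparison: it matches Baseline to Week 12 and the roughly 3 months of drug release. There is no formal testing of adverse-event incidence, so this is a matter of display.

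Most of that stands. A reader might infer from the pooled list that events more than 12 weeks after re-dosing go unreported, or that the plan never looks at the full period. The documents do not support either reading. Late events fall within Baseline to Week 52 in all ten tabulations, their terms appear in the by-visit tables for the four groups, and the listings date them from dose 2.

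The objection does not supply two things: a stated pooled second-dose figure over full follow-up, and any table showing which drug-related, procedure-related, severe or index-knee terms occurred late after dose 2. For those, the reader has to work through listings. The mixing argument is a reason to add a rate, and the by-visit tables can stay beside it.

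**Conclusion.** The point holds as a gap in presentation, of optional to moderate priority. In the pooled two-dose tables the only column starting at dose 2 covers 30% to 43% of planned follow-up for re-dosing at Weeks 12 to 24, assuming full follow-up to Week 52. Six tabulations have neither a later second-dose period nor a dedicated listing beyond the general data listings. Patients whose second dose falls outside the four groups have no by-visit adverse-event table.

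It would be tempting to read the 57% to 70% outside the column as a share of events missed, or to call the result biased. Neither follows. These are shares of time, the documents give no event timing, and no estimate is distorted.

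The conclusion rests on the SAP text. The table shells are in a separate document that was not available and might already contain the column.

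**What to change.** Add one column to the pooled two-dose tables: second dose to Week 52 or last contact. Date it from the actual second injection, not the mapped visit. Include every two-dose patient, also those re-dosed after Week 24, and use the actual number of two-dose patients as the denominator. Apply it to the summary tables and the tabulations, giving priority to the drug-related, procedure-related, maximum-severity and index-knee ones.

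For the summary rows, show beside n (%) the number of patients with a first event per 100 person-years after dose 2, because follow-up differs by re-dosing visit. Last contact is a workable end point: Protocol 7.4.4 already allows adverse-event follow-up to Week 52 for re-dosed patients who leave early and agree to be contacted.

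Keep the matched 12-week columns and the by-visit tables.

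The cost is SAP wording and table shells, using data already collected. The downside is wider tables and a crude percentage at least as high as in the 12-week column, and usually higher, which the rate helps the reader to interpret.
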